2.4. Statistical Interim analyses and stopping guidance

An interim analysis will be done after 10 patients. In the interim analysis, the agreement between the images obtained with the handheld ultrasound and the images on the gold standard device will be compared after the blinded scoring. A moderate level of agreement (defined as a kappa value of >0.40) between the two tools in the interim analysis will allow parallel initiation of subsequent studies proposed in the research framework. The results of this interim analysis will not be used to adjust the design of the remainder of the study. We do not have any formal stopping rules for the trial.

2.5. Timing of final analysis

After all sites recruit 10 patients each, the data will be verified and locked. Final analysis will commence once the final lock has been confirmed by the Principal Investigator.

2.6. Timing of outcome assessment

First outcome assessment will be made when 10 patients are included in the study for interim analysis. The final outcome assessment will be made when the planned total number of patients is reached.

3. Statistical Principles

3.1. Confidence Intervals and P-values

We will consider $p < 0.05$ statistically significant for our outcomes. Results will be presented with their values with the 95% confidence interval.

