2.3. Sample Size

Study agreement analyses will be done per joint. To give a kappa ≥ 0.61 (from substantial interrater agreement to almost perfect agreement) with a confidence interval width of 0.15 and the expectation of approximately 20 % of joints assessed having any synovitis in B mode (based on a previous study by our group), 683 joints would be required.⁴ This corresponds to 30 patients if 24 joints per patient are assessed. Non-inferiority margin will be $\kappa \geq 0.61$.

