5.2. Analysis Methods

Demographic, clinical and disease characteristics of patients will be presented using descriptive statistics. Numeric data showing normal distribution will be shared with mean and standard deviation, and those without normal distribution will be shared with median and interquartile range. Categorical data will be shared with numbers and percentages.

The primary endpoint analysis will be the interrater agreement of detecting any synovitis in B mode with the Clarius and gold standard machine. The kappa coefficients will be evaluated using the guideline outlined by Landis and Koch, where the strength of the kappa coefficients are: 0.01-0.20 slight; 0.21-0.40 fair; 0.41-0.60 moderate; 0.61-0.80 substantial; 0.81-1.00 almost perfect.⁷

For secondary outcomes, the interrater agreement for the presence of Doppler signals within the joints, tenosynovitis, erosions, nail, as well as features of enthesitis (hypoechoicity, thickening, erosions, enthesophytes, calcifications) will also be evaluated using the same method. The agreement of the semiquantitative grading of the intraarticular findings' severity (synovitis in B mode, Doppler signals, erosions, each being on a scale between 0-3) will be done using weighted kappa analysis.⁸

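### SAP 3.1 sets p < 0.05 for kappa outcomes without stating a null or linking the p-value or the 95% CI to the 0.61 margin; the usual kappa = 0 test would not address the agreement question.

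*SAP*

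**What the plan says.** SAP 3.1 has two sentences. The first is the rule "We will consider $p < 0.05$ statistically significant for our outcomes". The second promises intervals: "Results will be presented with their values with the 95% confidence interval". Neither names a hypothesis, a test or a sidedness.

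SAP 5.2 lists the analyses.
- Primary: "The primary endpoint analysis will be the interrater agreement of detecting any synovitis in B mode with the Clarius and gold standard machine", measured by kappa and read against the Landis and Koch bands ("0.01-0.20 slight; 0.21-0.40 fair; 0.41-0.60 moderate; 0.61-0.80 substantial; 0.81-1.00 almost perfect").
- Secondary presence/absence findings: these "will also be evaluated using the same method".
- Graded joint findings: agreement "will be done using weighted kappa analysis".
- Everything else is descriptive: "Demographic, clinical and disease characteristics of patients will be presented using descriptive statistics".

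The study has a single arm (SAP 2.1), and SAP 5.2 plans no group comparison to which a p-value could otherwise apply. Protocol 4.4 plans the same kappas and gives no null value.

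A benchmark does exist elsewhere. SAP 2.3 says "Non-inferiority margin will be" a kappa of at least 0.61. It does not say whether the estimate or its lower confidence limit must reach that value, and SAP 3.1 and 5.2 do not refer to it.

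**The concern.** A p-value needs a null. For kappa, the one usually printed tests kappa = 0, meaning agreement no better than chance. The objectives in SAP 1.2 ask something else: whether the handheld devices are as accurate as the reference machine. Rejecting chance agreement does not answer that and gives no support to the 0.61 margin.

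At stake is the labelling of results. The word significant could be attached to a kappa that SAP 5.2 classes as slight or fair, next to objectives phrased as equal accuracy. A reader of the report could take the label as evidence of equivalence. For the primary outcome, the plan would also leave open how its one stated margin is to be tested.

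**Working it through.** **Inputs.** Target kappa 0.61, full confidence interval width 0.15, 20% of joints positive, 683 joints, 30 patients with 24 joints each (SAP 2.3); 20 entheses and 4 tendons per patient (protocol 4.3); one nail and its contralateral, so 2 per patient (protocol 4.3); probes by joint (SAP Table 1, read as bilateral). The documents give no intraclass correlation (ICC), so a range is assumed.

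**1. The plan's own figure.** For two binary ratings with the same positive rate p, the large-sample variance of kappa is V/n, with

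V = (1−κ)[(1−κ)(1−2κ) + κ(2−κ)/(2p(1−p))].

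At κ = 0.61 and p = 0.20: V = 0.39 × [0.39 × (−0.22) + 0.8479/0.32] = 0.39 × 2.5639 = 0.9999. Then n = 4 × 1.96² × 0.9999/0.15² = 682.9, rounded up to 683. The stated figure reproduces. It is a precision calculation, not a power calculation against 0.61.

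**2. Threshold if the null is kappa = 0.** With both devices 20% positive, chance agreement is 0.2² + 0.8² = 0.68. The null variance is [0.68 + 0.68² − (0.04 × 0.4 + 0.64 × 1.6)]/(1 − 0.68)² = 0.1024/0.1024 = 1, divided by n. The smallest kappa with two-sided p < 0.05 is therefore 1.96/√n.

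| Sites | n | Smallest significant kappa | Band |
|---|---|---|---|
| All joints, 30 × 24 | 720 | 0.073 | slight |
| L20 joints, 30 × 16 | 480 | 0.089 | slight |
| L15 joints, 30 × 12 | 360 | 0.103 | slight |
| Entheses, 30 × 20 | 600 | 0.080 | slight |
| Tendons, 30 × 4 | 120 | 0.179 | slight |
| Nails, or one tendon type, 30 × 2 | 60 | 0.253 | fair |

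Equal positive rates on the two devices give 1/n whatever the rate, so the rows for other lesions do not depend on the 20%. The formula is for unweighted kappa; no threshold is derived for the graded outcomes.

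**3. What such a kappa means.** At κ = 0.075 and 20% positives on both devices, the share positive on both is 0.04 + 0.075 × 0.16 = 0.052. The handheld then finds 0.052/0.20 = 26% of the joints positive on the reference machine, against 20% by chance. With 720 joints, z = 0.075 × √720 = 2.01 and p = 0.044.

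**4. Several joints per patient.** With design effect 1 + 23 × ICC, the threshold at 720 joints is 1.96 × √(design effect/720):

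| Assumed ICC | Design effect | Threshold |
|---|---|---|
| 0.05 | 2.15 | 0.107 |
| 0.10 | 3.30 | 0.133 |
| 0.20 | 5.60 | 0.173 |
| 0.30 | 7.90 | 0.205 |

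It stays in the slight band until the ICC is nearly 0.3.

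**5. Threshold if the interval is tied to 0.61.** Find the smallest observed kappa whose lower two-sided 95% limit is at least 0.61. At κ = 0.678, V = 0.865, the standard error at 720 joints is √(0.865/720) = 0.0347, and 0.678 − 1.96 × 0.0347 = 0.610. So about 0.68 is needed, against 0.073 for a test of zero.

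**The case against.** The strongest reply is that p < 0.05 is not how this plan interprets agreement. SAP 5.2 reads the primary kappa, and by the same method the binary secondary kappas, against the Landis and Koch bands. SAP 3.1 itself requires 95% intervals. The other decision values also concern the size of kappa: above 0.40 at the interim (SAP 2.4) and at least 0.61 (SAP 2.3). A kappa of 0.07 would be shown with its interval and called slight.

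This stands, and it rules out three stronger readings that a reader might infer.
- That the trial would be declared successful at 0.07. Nothing in the documents turns p < 0.05 into a conclusion of equal accuracy.
- That the SAP specifies a test of kappa = 0. It names no null. Zero is the customary default, and for the primary outcome a null at 0.61 would be an equally natural reading of SAP 2.3.
- That p < 0.05 is the only yardstick for the secondary outcomes. The bands apply to the binary ones, and intervals are required for all.

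It is also fair that 0.07 is a floor. It pools both probes and treats joints as independent.

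The reply does not supply the missing null, and it does not connect the p-value or the interval to 0.61. The bands are descriptive labels, so SAP 3.1 remains the only place that defines what may be called significant, and it does so for all outcomes.

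**Conclusion.** The point holds as an undefined hypothesis with no link to the plan's own margin. Under the customary default, the significance label would be earned at a kappa of about 0.07 with 720 independent joints, 0.09 to 0.10 for each probe, and about 0.11 to 0.21 for ICCs of 0.05 to 0.30, while the margin is 0.61. The label would be uninformative for the objectives and could mislead beside them, but it would not override the bands or the intervals.

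The size rests on three assumptions: that the analyst tests kappa = 0, that both devices have the same positive rate, and that the ICC lies in the assumed range. The finding that no null is stated, and that nothing ties the p-value or the interval to 0.61, rests on none of them.

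**What to change.** Replace the p < 0.05 sentence in SAP 3.1 with:

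> Agreement is reported as kappa with its 95% CI, allowing for several sites per patient; no p-value against kappa = 0 is reported. For the primary outcome, the margin is met if the lower limit of the two-sided 95% CI is at least 0.61. Secondary kappas are reported with 95% CIs and Landis-Koch bands, without a significance statement.

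This needs no new data, and SAP 3.1 already promises the intervals. There are two costs, which should be stated openly.

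- **The primary criterion is demanding at the planned size.** The 683 joints were chosen for an interval width of 0.15, not for power against 0.61. An observed kappa of about 0.68 is needed at 720 independent joints. If the true kappa were 0.70, the standard error would be √(0.817/720) = 0.0337, and the chance of meeting the criterion about Φ((0.700 − 0.678)/0.0337) = Φ(0.65), or 74%; it is about 69% if the limit is computed with the standard error at 0.61. Clustering raises the bar: at an assumed ICC of 0.10, the equivalent of 720/3.3 = 218 independent joints, solving the equation in step 5 gives about 0.73.
- **Secondary results lose the significance label.**

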3.2. Adherence and protocol compliance

Attention will be paid to compliance with the protocol at every stage of the study. 100% compliance with the protocol is required. All data will be evaluated twice for protocol compliance. US images and CRFs uploaded from each center will be reviewed by the research assistant at Ottawa Hospital Research Institute (OHRI) center. If there are any missing or erroneous data in the CRF copy, research assistant will contact the site to ensure that the errors and deficiencies are corrected in source document according to Good Documentation Practice. Site should then re-scan the CRF to the SharePoint, ensuring sequential versioning. Any queries will be confirmed with the site within a week of the data entry. Then the analyzed CRFs data will be transferred to Research Electronic Data Capture (REDCap) (version 12.4.18 - © 2023 Vanderbilt University) by the research assistant at OHRI. Before each analysis (interim and final), all the paper CRFs and REDCap data will be compared for quality assurance. Twenty percent of data monitoring will be performed, as per monitoring plan. If a protocol violation is detected in obtaining any data, this data will be documented and retained in records.

3.3. Analysis populations

All patients will be included in the analysis.

4. Trial Population

4.1. Eligibility

Adult patients with peripheral PsA who are not in minimal disease activity (MDA) and show at least one tender and swollen joint are eligible for study.

Inclusion Criteria

- Age ≥ 18
- Meets the classification for psoriatic arthritis (CASPAR) criteria
- Able to provide an informed consent
- Having peripheral disease phenotype of PsA
- At least one tender and swollen joint on the day of US

Exclusion Criteria

- Having isolated axial PsA
- Being in MDA with no tender and swollen joints

4.2. Withdrawal/Follow-up

There are no follow-up visits in the study, therefore we do not expect a withdrawal.

4.3. Baseline Patient Characteristics

There will be only one study visit and the following data will be collected at the baseline visit.

- Patient's age
- Gender
- Body Mass Index (BMI)
- Physical activity
- Smoking
- Treatments and disease activity
- 66/68 joint count for tender and swollen joints
- Spondyloarthritis Research Consortium of Canada (SPARCC) enthesitis index,
- Number of dactylitic digits,
- Body surface area for skin disease
- Presence of nail disease
- Pain Visual Analogy Scale (VAS),

- Patient global assessment
- Health Assessment Questionnaire Disability Index (HAQ-DI)
- Erythrocyte sedimentation rate (ESR)
- C-Reactive Protein (CRP)
- Adverse events related to ultrasound scanning

5. Analysis

5.1. Outcome Definition

5.1.1. Primary Outcome

After the imaging of all patients is completed, intraarticular synovitis scoring will be done based on the OMERACT definitions (scales of 0-3) as follows, for the anatomical sites given in Table 1.^{5,6}

Greyscale inflammatory (hypoechoic) synovial hyperplasia:

Grade 0: no hypoechoic synovial hyperplasia

Grade 1: minimal hypoechoic synovial hyperplasia (filling the angle between the periarticular bones, without bulging over the line linking tops of the bones)

Grade 2: hypoechoic synovial hyperplasia bulging over the line linking tops of the periarticular bones but without extension along the bone diaphysis

Grade 3: hypoechoic synovial hyperplasia bulging over the line linking tops of the periarticular bones and with extension to at least one of the bone diaphysis

Table-1:Probes/scanners, views and anatomical sites for primary outcomes

Anatomical site	Views	GE Logic E9/S8	Clarius L15	Clarius L20
2nd MCP joints	dorsal and lateral	X	X	X
3rd MCP joints	dorsal	X		X
2nd-3rd PIP, 2nd-3rd DIP	dorsal	X		X
Wrist	dorsal	X	X	X
5th MTP joints	dorsal and lateral	X		X
Elbow joints	posterior	X	X	
Shoulder joints	posterior	X	X	
Knee joints	anterosuperior	X	X	
Ankle joints	anterior	X	X	

5.1.2. Secondary Outcomes

5.1.2.1. Joints

After the imaging of all patients is completed, the intraarticular Doppler scoring will be done based on the OMERACT definitions (scales of 0-3) (Table 1):^{5,6}

Power Doppler signal:

Grade 0: no flow in the hypoechoic synovial hyperplasia

Grade 1: up to three single spots signals or up to two confluent spots or one confluent spot plus up to two single spots

Grade 2: vessel signals in less than half of the area of the synovium ($\leq 50\%$)

Grade 3: vessel signals in more than half of the area of the synovium ($> 50\%$)

Also, a lateral view of the 2nd metacarpophalangeal and 5th metatarsophalangeal joints will be recorded in the baseline visit for erosion assessment. Erosions will be described as intra-articular discontinuity of the bony surface seen in 2 perpendicular planes and will be evaluated after the imaging of all patients is completed.

5.1.2.2. Nails

B mode and doppler images of the 2nd nail or most involved nail with all probes (Clarius L20, GE Logic E9/S8) will be recorded in the baseline visit. The loss of the trilaminar appearance and the presence of doppler signal in the nail will be evaluated after the imaging of all patients is completed. During imaging of the nail, if any Doppler signal is detected in nail bed, regardless of its severity, the presence of Doppler signal will be considered positive.

5.1.2.3. Tendons

B mode and Doppler images of the tibialis posterior tendon with Clarius L15 and GE Logic E9/S8 will be recorded in the baseline visit. The presence of tendonitis, tenosynovitis and intratendinous Doppler signal in tibialis posterior tendon will be evaluated after the imaging of all patients is completed. Tendonitis will be defined as loss of fibrillary echotexture with hypoechoogenicity within the tendon fibres on B-mode (regardless of the presence of Doppler signal). Tenosynovitis will be defined as characterized by hypoechoic or anechoic thickened tissue with or without fluid in the tendon sheath on B-mode (regardless of the presence of Doppler signal). If any Doppler signal is detected in tendon, regardless of its severity, the presence of intratendinous Doppler will be considered positive.

B mode and Doppler images of the 2nd extensor digitorum tendon with Clarius L20 and GE Logic E9/S8 will be recorded in the baseline visit. The presence of paratenonitis and intratendinous Doppler signal in the extensor digitorum tendon will be evaluated after the imaging of all patients is completed. Paratenonitis will be defined as the lack of a sheath on the extensor tendon above the metacarpophalangeal joint with accompanying inflammatory changes to the extensor tendon consisting of increased thickness, loss of fibrillary echotexture, with or without power Doppler signal. If any Doppler signal is detected in the tendon or the tendon sheath, regardless of its severity, the presence of intratendinous Doppler will be considered positive.

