1.2. Objectives

Our aim to test the concurrent validity of the Clarius handheld US devices versus gold-standard device to detect characteristic features of healthy and rheumatic joints (i.e. anatomical structures and vascular flow.

Primary objective:

To determine whether handheld US devices (Clarius HD3 L20 and L15 scanners) B mode are as accurate as gold standard device (GE Logic E9/S8) at visualizing intraarticular synovitis

Secondary objectives:

1. To determine whether handheld US devices (Clarius HD3 L20 and L15 scanners) power Doppler mode are as accurate as gold standard device (GE Logic E9/S8) at detecting intrasynovial signals
2. To determine whether handheld US devices (Clarius HD3 L20 and L15 scanners) B mode are as accurate as gold standard device (GE Logic E9/S8) at visualizing tenosynovitis
3. To determine whether handheld US devices (Clarius HD3 L20 and L15 scanners) power Doppler mode are as accurate as gold standard device (GE Logic E9/S8) at detecting intratendineous signals
4. To determine whether handheld US devices (Clarius HD3 L20 and L15 scanners) B mode are as accurate as gold standard device (GE Logic E9/S8) at visualizing bone erosions
5. To determine whether handheld US devices (Clarius HD3 L20 and L15 scanners) B mode are as accurate as gold standard device (GE Logic E9/S8) at grading intraarticular synovitis
6. To determine whether handheld US devices (Clarius HD3 L20 and L15 scanners) power Doppler mode are as accurate as gold standard device (GE Logic E9/S8) at grading intrasynovial signals
7. To determine whether handheld US devices (Clarius HD3 L20 and L15 scanners) B mode are as accurate as gold standard device (GE Logic E9/S8) at grading bone erosions
8. To determine whether handheld US devices (Clarius HD3 L20 and L15 scanners) power Doppler mode are as accurate as gold standard device (GE Logic E9/S8) at visualizing elementary lesions of enthesitis

9. To determine whether handheld US devices (Clarius HD3 L20 and L15 scanners) power Doppler mode are as accurate as gold standard device (GE Logic E9/S8) at detecting entheseal signals
10. To determine whether handheld US devices (Clarius HD3 L20 and L15 scanners) B-mode are as accurate as gold standard device (GE Logic E9/S8) at detecting trilaminar appearance of the nail plate abnormalities

2. Study Methods

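### The L20's only B-mode tendon outcome scores no sign around the tendon, so B-mode-only change there cannot register and the L20 cannot inform objective 2

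*SAP*

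**What the plan says.** SAP 5.1.2.3 covers two tendons, one per handheld probe.

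- **Tibialis posterior (L15).** "B mode and Doppler images of the tibialis posterior tendon with Clarius L15 and GE Logic E9/S8 will be recorded". It is read for two separate B-mode lesions. One lies inside the tendon: "Tendonitis will be defined as loss of fibrillary echotexture with hypoechoogenicity within the tendon fibres on B-mode". The other, tenosynovitis, lies around it: "hypoechoic or anechoic thickened tissue with or without fluid in the tendon sheath on B-mode". Doppler is read as well.
- **Second extensor digitorum (L20).** "B mode and Doppler images of the 2nd extensor digitorum tendon with Clarius L20 and GE Logic E9/S8 will be recorded". "The presence of paratenonitis and intratendinous Doppler signal in the extensor digitorum tendon will be evaluated". There is one B-mode outcome: "Paratenonitis will be defined as the lack of a sheath on the extensor tendon above the metacarpophalangeal joint", together with "accompanying inflammatory changes to the extensor tendon consisting of increased thickness, loss of fibrillary echotexture, with or without power Doppler signal". The next sentence makes the Doppler outcome positive for any signal in this tendon or in its sheath.

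Protocol Table-2 gives the same probe split. The L20 also images the Achilles insertions and the extensor insertions at the DIP and PIP, but SAP 5.1.2.4 scores these as entheses. The protocol does not define paratenonitis.

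Secondary objective 2, in both documents, asks whether the L20 and L15 in "B mode are as accurate as gold standard device (GE Logic E9/S8) at visualizing tenosynovitis". SAP 5.2 lists tenosynovitis among the kappa outcomes but does not list paratenonitis.

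**The concern.** For the tibialis posterior the SAP separates change inside the tendon from change around it. For the extensor tendon it does not. Absence of a sheath describes anatomy and is not a sign of inflammation. Thickening and loss of fibrillar pattern are signs in the tendon itself, and the second is shared with the SAP's own tendonitis definition. Nothing corresponds to the tenosynovitis sign.

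In a device-agreement study an outcome is useful only if it can register a difference between the devices. Here a B-mode finding around the tendon that one machine shows and the other does not leaves no trace. Objective 2 claims B-mode accuracy around tendons for both probes, and for the L20 no planned score would support or contradict that claim.

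**Working it through.** **1. What each outcome can register.** The SAP rules applied literally to one extensor tendon, written as GE score / L20 score (1 = positive):

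| GE shows | L20 shows | Paratenonitis as written | Doppler outcome | Separate score for tissue around tendon |
|---|---|---|---|---|
| Tissue around tendon, normal fibres, no Doppler | The same | 0/0 | 0/0 | 1/1 |
| Tissue around tendon, normal fibres, no Doppler | Nothing | 0/0 | 0/0 | 1/0 |
| The same tissue, with Doppler around the tendon read as sheath signal | Nothing | 0/0 | 1/0 | 1/0 |
| Fibrillar loss without thickening, no Doppler | The same | 1/1 if either sign suffices, 0/0 if both are required | 0/0 | 0/0 |

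Rows 1 and 2 are the point: the L20 differs, and neither planned outcome changes. Row 3 is the part the Doppler rule covers. Row 4 shows that the two tendon signs are listed without saying whether one or both are needed.

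**2. Illustration of size (assumed counts).** There are 2 extensor tendons × 30 patients = 60. The cells are a = both positive, b = GE only, c = L20 only, d = both negative, and

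kappa = (po − pe)/(1 − pe), with po = (a + d)/60 and pe = [(a + b)(a + c) + (c + d)(b + d)]/3600.

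Assume 6 tendons meet the paratenonitis criteria on both machines and 12 others have Doppler-negative tissue around the tendon, with normal fibres, on GE.

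- Paratenonitis as written: (6, 0, 0, 54), kappa 1.00, whether the L20 shows all, some or none of the 12.
- Sign around the tendon, 6 of 12 seen: (6, 6, 0, 48). po = 0.90, pe = (72 + 2592)/3600 = 0.74, kappa = 0.16/0.26 = 0.62.
- Sign around the tendon, 0 of 12 seen: (0, 12, 0, 48). po = pe = 0.80, kappa = 0. This is automatic when one machine never scores positive, so it is the limit of the range and not an expectation.
- Either sign, 6 of 12 seen: (12, 6, 0, 42). po = 0.90, pe = 0.62, kappa = 0.74.
- Either sign, 0 of 12 seen: (6, 12, 0, 42). po = 0.80, pe = 0.66, kappa = 0.41.
- Either sign, none seen, with 6 or 18 such tendons instead of 12: kappa 0.62 or 0.29.

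**3. Precision of an L20 tendon result.** The plan gives no sample-size figure for tendons. Its figure for joints reproduces with V = (1 − k)[(1 − k)(1 − 2k) + k(2 − k)/(2p(1 − p))] and n = 4z²V/w². At k = 0.61 and p = 0.20, V = 0.39 × [0.39 × (−0.22) + 0.8479/0.32] = 1.000. With w = 0.15 and z = 1.96, n = 682.9, which rounds up to the stated 683. For 60 tendons at k = 0.61, the 95% interval width 2z√(V/60) is about 0.51 at an assumed prevalence of 20% and 0.68 at 10%, ignoring clustering within patients. Any L20 tendon kappa will therefore be imprecise.

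**The case against.** **The Doppler rule.** A reader might infer that all inflammation around the tendon missed by the L20 counts as agreement, or that the extensor images say nothing about such inflammation. The documents do not support that. The Doppler rule for this tendon extends to its sheath, so a signal there on GE and no signal on the L20 is a disagreement on a planned outcome. This stands, and it confines the point to Doppler-negative change. The cover is only partial: the rule refers to a sheath that the definition says is lacking, and a Doppler outcome does not answer a B-mode objective.

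**The criteria.** A reader might also infer that fibre change alone is scored as paratenonitis, making it tendonitis under another name. That holds only if one of the two signs suffices. If both are required, the outcomes differ, because tendonitis has no thickness criterion. The text leaves this open.

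**The definition.** The documents do not establish one correct definition of paratenonitis. It is therefore safer to add a score than to replace the definition.

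**The objective.** Objective 2 could be read as covering the two handhelds jointly, with the L15 supplying the tenosynovitis result. The SAP does not say so, and the objective names both scanners.

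**Weight.** The same definition and the same reader apply to both machines, so kappa remains a fair comparison for the sign as defined. This is one lesion at one site under one of ten secondary objectives, and the primary outcome is untouched.

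An experienced reader might score the tissue around the tendon anyway, but that would be an unwritten rule that could not be reproduced from the SAP.

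**Conclusion.** The point holds for Doppler-negative B-mode change around an extensor tendon that does not meet the listed tendon criteria. As the SAP is written, such change is negative on both machines, and the L20 has no B-mode outcome that bears on objective 2. This follows from the wording and needs no assumption beyond a literal reading.

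The size is unknown. The kappa values above rest wholly on assumed counts. They show what the outcome cannot detect, and they do not predict what the study would find. The finding does not extend to Doppler-positive change, to the validity of the paratenonitis kappa for the sign as defined, or to the primary analysis. It is a worthwhile, low-cost improvement to a secondary outcome.

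**What to change.** In SAP 5.1.2.3:

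1. Add a separate present/absent B-mode score for thickened tissue, hypoechoic or anechoic, around the extensor tendon, parallel to the tenosynovitis wording. Score it on the L20 and GE images, and report its kappa with a 95% confidence interval as the L20 result for objective 2.
2. Score tendon thickening and fibrillar loss separately, and state whether paratenonitis requires both.
3. Reconcile the absence of a sheath in the definition with the Doppler rule that counts signal in the sheath of the same tendon.

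In SAP 5.2, list the added score and paratenonitis among the kappa outcomes.

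The cost is SAP wording and one extra score for tissue around the tendon per extensor-tendon image, plus recording the two tendon signs separately. Protocol 4.3 already requires at least one B-mode and one power Doppler image per site, so no new scans are needed. The wording should be settled before the images are scored.
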